#### **4.3.c Recruitment of 36 Communities in 6 Counties into the Testing Program**

This testing program will build on existing partnerships with 6 county public health authorities in Oregon (see letters of support), that are either designated as a rural county by the Office of Management and Budget (Lincoln, Douglas, Josephine) or have a significant rural population (Lane, Marion, Benton). We will establish contracts with each county to provide them with staffing resources to support additional testing in Latinx communities. In addition, we will work with each county public health agency to develop a County Collaborative that includes key community stakeholders in the Latinx community, including those representing Latinx serving organizations such as non-profits and churches. The focus of the County Collaboratives is to engage the implementation process described in the implementation strategy. Leveraging the county collaboratives' knowledge of county communities, 6 communities (identified by zip code or zip code cluster) within each county will be selected for site implementation. Given that proximity is a critical component for reducing barriers to access in rural communities, and given the composition of the 6 counties, most of the 36 communities who participate in the testing program will be rural. We will employ *a priori* stratification by county and rurality to balance potential confounders, to reflect the hierarchical structure of the design in the analytic plan. Specifically, for the first randomization, within each county, 3 communities will be randomized to the treatment condition and 3 to the control condition (total of 18 per condition, 36 total).

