#### **4.3.d Data Analysis for Aims 1 and 2**

For the primary evaluation aims for determining the optimal strategy for testing Latinx communities and the four adaptive intervention strategies, we will employ standard normal theory generalized linear modeling analysis of covariance fractional factorial analyses using pre-post assessment scores for site and individual level outcomes. Research Question 1 will focus on the combined effects of A1 randomization groups [(A+B+C+D) vs (E+F+G+H)]. Research Question 2 will focus on which A2 strategy works best for slow-responding sites [(D+H) vs (C+G)]. To address the non-independence of subjects in the embedded adaptive intervention designs and crossed factors, we will estimate linear mixed models with weighted least squares using the design effects coding shown in Table 4.3.1.

The general equation to estimate the optimal strategy is given by

$$E[Y|A_1, A_2, O_1] = \beta_0 + \beta_1 A_1 + \beta_2 A_2 + \beta_3 A_1 A_2 + \gamma^T O_1$$

where  $E$  is the expected value of the outcome,  $A_1$  is the initial treatment randomization,  $A_2$  is the second stage treatment randomization and  $\gamma^T$  are the estimates for covariate  $O_1$ , the pre-test covariate. For binary and count data we will employ generalized linear modeling and logit, probit, and poisson link functions for criterion outcomes such as frequency of tests, re-tests, and discrete event behaviors.

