#### 4.3.f Power

Power for detecting the optimal AIS was estimated using the SMARTAR package 1.0.0 in R R^71. We chose a power convention of .80 with a two-sided alpha level of .05 to reduce the probability of obtaining a false positive (Type-I error). For research question 1, balanced response rates of 50% of sites having adequate response and 50% slow responding, 36 sites for a continuous outcome (e.g., rates) can minimally detect a small difference of .27 among the combined group comparisons [(A+B+C+D) vs (E+F+G+H)], and power to minimally detect a medium effect of .54 (n=18 sites) [(D+H) vs (C+G)]. For the global test of the optimal treatment strategy (n=36 sites), the study is powered to minimally detect an effect of .40, a moderate effect. Power for detecting the optimal AIS was estimated using the SMARTAR package 1.0.0 in R^71.

We must also consider response scenarios that include either more slow-responding or even less slow responding sites before the tailoring intervention (i.e., 80% of the randomly allocated sites responded at capacity and 20% were below threshold; or alternatively, only 20% responded and 80% were below capacity initially). In each of these "unbalanced" response scenarios, power for research question 1 is the same as the balanced design above. Although we do not anticipate such a large range of slow responding sites based on our preliminary testing; for the slow-responding sites only, a bracket range of 80/20 response ratio (resulting in 8 slow responding sites [(D+H) vs (C+G)]) to a high of 20/80 ratio (resulting in 28 slow responding sites [(D+H) vs (C+G)]). In these scenarios, for research question 2, the study is powered .80 to minimally detect a difference of 1.3 (a large effect) or to minimally detect a moderate effect of .35 (a moderate effect), respectively, for 8 to 28 total slow responding sites for research question 2.

[figure not shown]

Figure 4.3.f Power Curve.

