Finally, when considering power for individual level data, a mixed model with two levels (individuals nested within sites) we must consider full capacity scenarios where implementation is realized at full capacity (roughly 3600 tests) to scenarios that obtain a smaller number of individual tests based on response patterns by site. In this case, that is the balanced scenario shown in Figure 4.3.1 given half of the sites are slow responding. That scenario projects a maximum of 2520 level-1 testing units sampled from 36 sites and achieves .80 power to detect a difference of .22 (a small effect) among the group conditions for randomization 1 conditions A1, randomization 2 conditions A2, and their crossed A1A2 interaction, and an intraclass correlation of .05 for the test of comparative intervention strategies from the primary equation shown above. Thus, the study is adequately powered for all multilevel data scenarios for minimum response to maximum response to detect small effect sizes. Power for individual comparisons among the 4 embedded AISs is shown in Figure 4.3.f.

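### The stated .80 power at .22 for individual outcomes needs an unstated gain (the inputs give 70 to 75%), and Question 2 among slow sites has no individual-level power in the text

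*SAP*

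**What the plan says.** SAP section 4.3.f sets "a power convention of .80 with a two-sided alpha level of .05". For individual-level data it assumes people nested within sites. Its balanced scenario, with half the sites slow to respond, has "a maximum of 2520 level-1 testing units sampled from 36 sites" and "an intraclass correlation of .05 for the test of comparative intervention strategies from the primary equation shown above". It concludes that this "achieves .80 power to detect a difference of .22 (a small effect) among the group conditions for randomization 1 conditions A1", and likewise for A2 and the A1A2 interaction. It then states that "the study is adequately powered for all multilevel data scenarios for minimum response to maximum response to detect small effect sizes".

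Two features of the plan could improve precision. The model equation in 4.3.d includes a pre-test covariate. Section 4.3.c plans "stratification by county and rurality to balance potential confounders, to reflect the hierarchical structure of the design in the analytic plan". Neither is given an R-squared, a correlation or a share of variance explained.

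Question 2 is a different contrast. Sections 4.3.b and 4.3.d define it among slow-responding sites only, as (D+H) against (C+G). In the opening paragraph of 4.3.b, Question 2 covers individual health behaviors and site testing capacity. The restated question and Aim 2 name site testing capacity only.

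**The concern.** A reader who puts the stated inputs into the usual cluster formula does not get .80 at .22, so some input is missing from the text.

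The second issue matters more. Section 4.3.f gives site-level detectable differences for Question 2 with 8, 18 and 28 slow sites. Its individual-level text has no counterpart, yet it ends with a claim about all multilevel scenarios. The A2 figure there rests on all 36 sites and 2,520 people, not on the slow subset.

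Section 4.3.a names individual COVID-19-related health behaviors among the primary outcomes, although Protocol section C names only site-level testing rates. The 4.3.f paragraph is the only individual-level power statement in the text. A null slow-site result on health behaviors could be read as coming from a comparison powered for small effects when it was not.

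**Working it through.** **Inputs.** Two-sided alpha .05 and power .80 (4.3.f); 36 sites, 18 per condition (4.3.c); 2,520 people, ICC .05 and difference .22 (4.3.f). Assumptions: .22 is in SD units, since no SD is given; there is no covariate or stratum gain; and, for A2 and the effect-coded A1A2 term, all 36 sites are re-randomized in balance, so that these contrasts also compare 18 sites with 18.

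**Formula.** With J sites per arm and m people per site, SE = sqrt(2 × (ICC + (1 − ICC)/m)/J). By the normal approximation, the detectable difference is (1.960 + 0.842) × SE and power is Φ(.22/SE − 1.960). Paired results below are normal approximation / noncentral t on 2J − 2 df.

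**The plan's own figure (.80 at .22).** Mean site size is 2,520/36 = 70.
- SE = sqrt(2 × (.05 + .95/70)/18) = sqrt(2 × .0636/18) = .0840.
- Power = Φ(.22/.0840 − 1.960) = .745; by t on 34 df, .720.
- Equivalently, the design effect is 1 + 69 × .05 = 4.45 and the effective sample is 2,520/4.45 = 566.

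**Site sizes (inferred).** 36 sites × 2 events × 50 tests = 3,600, or 100 per site at full capacity. If the 18 adequate sites test 80 to 100 each, the slow sites average (2,520 − 18 × 80)/18 = 60 down to (2,520 − 18 × 100)/18 = 40. Unequal sites are weighted by inverse variance.

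| Contrasts over 36 sites | Power at .22 | Detectable at 80% |
|---|---|---|
| 70 per site (2,520) | .745 / .720 | .236 / .242 |
| 18 sites of 80, 18 of 60 (2,520) | .743 / .719 | .236 / .243 |
| 18 sites of 100, 18 of 40 (2,520) | .730 / .705 | .240 / .247 |
| 100 per site (3,600) | .772 / .748 | .228 / .235 |

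A one-sided .05 test at 70 per site would give .835 / .821, but the SAP states a two-sided test.

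**Gain needed for .80 at .22 with 2,520 people.**
- R-squared acting on both levels: .127 / .176 at 70 per site and .157 / .205 at 100/40, so about .13 to .21 (correlation about .36 to .45).
- Or, at 70 per site, an ICC of .042 / .039.
- Or, at 70 per site, a cut in between-site variance of 16% / 22%.
- The level matters. At 70 per site the variance of a site mean is .05 + .95/70 = .0636, of which .05 (79%) is between sites. A covariate that explains only within-site differences would need an R-squared of .60 / .83. A within-site R-squared of .21 gives only .764 / .740.

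**Question 2, 18 slow sites (J = 9, t on 16 df), no covariate gain.** With unlimited people, SE = sqrt(2 × .05/9) = .1054.

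| People per slow site (assumed) | Power at .22 | Detectable at 80% |
|---|---|---|
| 40 | .405 / .365 | .359 / .382 |
| 60 | .444 / .401 | .339 / .361 |
| 70 | .457 / .413 | .333 / .355 |
| Unlimited | .551 / .501 | .295 / .315 |

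An R-squared of .13 to .21 on both levels, enough to close the 36-site gap, leaves power here at .41 to .55 for 40 to 70 people per site. Reaching .80 at .22 would need .56 to .67.

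**Other slow-site counts in 4.3.f, at 40 to 70 people per site.** With 8 slow sites, power at .22 is about 16 to 23%. With 28 it is about 54 to 64%, and 71 to 74% with unlimited people.

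**The case against.** The strongest reply is that the check above is not of the SAP's own model. Section 4.3.f ties its figure to the primary equation, which contains a pre-test covariate, and an R-squared of .13 to .21 is modest. This stands as far as it goes: .22 may be attainable, and a miscalculation is not proven. But the gain is not stated, nor is the level at which it acts. If the ICC of .05 and the effect of .22 are already conditional on the covariate, no further gain remains.

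The gap is also small, and .24 or .25 would still be called a small effect. That is right, and for the 36-site contrasts alone this would be a minor clarification.

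On Question 2, the .22 is never explicitly claimed for slow sites, two of the three wordings drop health behaviors, and the closing sentence may refer only to the range of test counts. These points have force. Yet 4.3.d applies its analysis to site and individual outcomes, and the opening paragraph of 4.3.b includes health behaviors in Question 2. Even on the narrow reading, 3,600 people do not give .80 at .22 without the unstated gain.

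Finally, Figures 4.3.1 and 4.3.f and the coding table were not available to this review and may hold per-site counts. The text describes Figure 4.3.f as covering comparisons among the four embedded strategies, which is not the slow-site contrast.

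**Conclusion.** The concern holds. The .80 power at .22 does not follow from the inputs given. With SD units, two-sided .05 and no covariate or stratum gain, power is 70 to 75% at 2,520 people and 75 to 77% at 3,600. At 2,520 the detectable difference exceeds .22 by only about .015 to .027 SD. This is an undocumented input rather than a demonstrated error.

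The consequence is greater for Question 2. With 18 slow sites, no covariate gain and ICC .05, power at .22 cannot exceed about 50 to 55%, and no difference below about .30 is detectable with 80% power. The illustrative 37 to 46% rests on an assumed 40 to 70 people per site. The ceiling does not depend on that assumption. The claim of adequate power in all multilevel scenarios is supported at most for contrasts over all 36 sites, and there only if the missing gain is documented or the difference restated.

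**What to change.** In SAP section 4.3.f:

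1. Restate the individual-level detectable difference for A1 as about .24 to .25 at 2,520 people and about .23 at 3,600. Alternatively, keep .22 and state the R-squared, ICC or stratum effect that yields it, and whether it acts between sites, within sites or both.
2. Say that the figure applies to contrasts over all 36 sites. For individual-level Question 2, either give a detectable difference from the sponsor's own per-site counts or state that the comparison is not powered for small effects.
3. Limit the adequacy sentence to comparisons over all 36 sites.

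In section 4.3.b, reconcile the three Question 2 wordings so that it is clear whether individual health behaviors belong to that question.

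The cost is SAP wording only. Design, sample size and analysis do not change. The power statement becomes slightly less favorable for A1, or gains a documented input, and becomes clearly less favorable for slow-site Question 2.
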